8. ADVERSE EVENTS

In this study, AEs will be reported for all subjects from signing of consent until the completion of the end of study Day 7 follow-up visit. SAEs will be reported in all subjects (enrolled and not enrolled) from the time of consent. Treatment-emergent AEs (TEAEs) will be reported from dosing on Day 0. Study procedure-related AEs will be evaluated specifically from the time of consent until INP103 or placebo administration. Treatment-emergent AEs will be evaluated from INP103 or placebo dosing until the end of study visit. AEs that are ongoing at the end of study visit will be marked as ongoing on the AE eCRF page.

All AEs resulting from spontaneous subject self-reporting, direct enquiry or observation by study staff, will be recorded in the subject's medical records and the eCRF.

8.1. Safety Monitoring Committee

Once dosing has been completed for all subjects in Cohort 1, a Safety Monitoring Committee (composed of the Principal Investigators, the contract research organization (CRO)'s Medical Monitor and the Sponsor's Medical Monitor) will review the AEs reported for the completed cohort. If they assess the benefit:risk ratio of the completed cohort acceptable, that decision will be documented, and the subsequent cohort given permission to proceed with dosing. This will be repeated for Cohort 2. No SMC meeting is planned following Cohort 3, unless safety concerns were raised during the SMC meetings occurring after Cohorts 1 and 2. The rationale for no SMC meeting prior to Cohort 4 is because the dose of L-dopa and DCI is less than for Cohort 3. However, all other usual safety monitoring will remain in place for the duration of the study.

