Cohorts will be enrolled and dosed in sequence. Escalation to the next higher dose cohort (Cohorts 1 to 2 and 2 to 3) may only commence after review and approval of safety data by a Safety Monitoring Committee (SMC). Interim analysis of data will be conducted upon completion of Cohort 1 and 2 study procedures, at the discretion of the Sponsor, depending on rate of recruitment. In this scenario, Cohort 1 and 2 data will be soft-locked, patients may be unblinded and tables, listings, and figures of collected data will be produced. Unblinding of Cohort 1 and 2 data will not jeopardise blinding of any enrolled Cohort 3 or 4 subjects at the time of the interim analysis.

Follow-up

Subjects will be monitored for 7 days after administration of INP103 or placebo. All subjects will be observed as in-patients for at least 240 minutes post-dosing. Follow-up

	
evaluations will occur 7 days after dosing. The SMC will have 7–14 days between dosing of Cohorts 1 and 2 and again between 2 and 3 to review safety data compiled by the site and contract research organization (CRO).

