Treatment Groups:	
Subjects will receive one of the following treatments:
 
All subjects in Cohorts 1, 2 and 3 will receive oral benserazide hydrochloride (benserazide) 25 mg at 60 ± 5 minutes prior to INP103 or placebo dosing and time recorded. Cohorts 1, 2 and 3 will comprise eight subjects total; six subjects in receipt of INP103 (L-dopa via I231 POD Device) and two subjects placebo (via I231 POD Device).
 
Cohort 4 will NOT receive oral benserazide. Cohort 4 will comprise of eight subjects; six subjects in receipt of INP103 (L-dopa with carbidopa via I231 POD Device) and two subjects placebo (via I231 POD Device). At the discretion of the Sponsor, depending on rate of recruitment, cohort 4 may be over enrolled with a total of up to 12 subjects using the 3:1 randomization scheme.
 
Cohort 1 (INP103 35 mg L-dopa total or placebo as one spray to one nostril): Each subject in this cohort will receive one dose of INP103 or placebo delivered by one actuation of the device.
 
Cohort 2 (INP103 70 mg L-dopa total or placebo as one spray to each nostril): Each subject in this cohort will receive one dose of INP103 or placebo delivered by two actuations of the device.
 
Cohort 3 (INP103 140 mg L-dopa total or placebo as two sprays to each nostril): Each subject in this cohort will receive one dose of INP103 or placebo delivered by four actuations of the device.
 
Cohort 4 (INP103 70 mg L-dopa/7.0 mg carbidopa total or placebo as one spray to each nostril): Each subject in this cohort will receive one dose of INP103 or placebo delivered by two actuations of the device, one to each nostril.
 
At 120 minutes post study dosing, subjects should take their usual anti-OFF medication (e.g. Madopar rapid) if they have not returned to ON, and their usual morning dose of PD medications (e.g. their regular Madopar® or Sinemet® morning dose). Subjects will remain under observation for another 120 minutes before they can be allowed to leave (health status permitting).
 
Escalation to Cohorts 2 and 3 may only commence after review and approval of safety data by a SMC (see Study Design, above) of Cohorts 1 and 2 respectively. There will be no SMC meeting between Cohorts 3 and 4 if there are no safety concerns raised by the SMC meetings occurring after Cohorts 1 and 2, since the dose of L-dopa and DCI in Cohort 4 is less than Cohort 3. However, all usual safety monitoring will remain in place.

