1.2. Summary of Non-Clinical and Clinical Studies

1.2.1. Non-Clinical Studies

Oral L-dopa has been extensively used in the treatment of PD and is supported by a literature evidence base. A review of literature is provided in the Investigator's Brochure. In addition, Impel NeuroPharma has performed the following studies:

- Six studies in the cynomolgus monkey examined the PK of powder L-dopa formulations, including two studies testing L-dopa formulations containing carbidopa, using a non-human primate version of the clinical POD Device (nhpPOD). The dose of L-dopa per nasal surface area varied from approximately 0.5 to 1.2 mg/cm², similar to the local nasal concentrations estimated to be achieved clinically (0.4375–0.875 mg/cm²) following doses of 35–140 mg L-dopa to the nose. No clinical observations were noted.

- Study 1: Following intranasal administration of unmodified crystalline L-dopa (of particle size $D_{50} = 50 \mu\text{m}$) in the absence of benserazide, dose-dependent PK was shown (10-40 mg dose range). The C_{max} following 40 mg L-dopa administration was 150 ng/mL, and the T_{max} was delayed, showing an average of ≥ 75 minutes. A smaller particle size (20-40 μm) crystalline L-dopa material was also tested and indicated a higher exposure compared to an equivalent dose of an unmodified L-dopa formulation.
- Study 2: The PK of intranasal L-dopa in combination with oral benserazide was explored (4 x 5mg administered over 24hr predose), demonstrating similar PK across four L-dopa formulations containing crystalline particle size sifted L-dopa (20-40 μm), spray dried L-dopa only (particle size D_{50} 10-30 μm), spray dried L-dopa with sodium chloride (L-dopa:NaCl) and spray dried L-dopa with sodium chloride and HPMC (L-dopa:HPMC:NaCl). C_{max} concentrations of >900 ng/mL were achieved following a dose of 20 mg (10 mg/nostril) of each formulation, which is above the threshold necessary for efficacy of OFF episode treatment. C_{max} was approximately 10-fold higher in the presence of benserazide. Median T_{max} was 45 to 60 minutes, an improvement over the T_{max} observed in the absence of benserazide.

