- Study 4: A fourth study determined PK of intranasal L-dopa in five spray dried formulations with a reduced concentration of maltoside (1% w/w) in combination with oral benserazide. All formulations contained 68% L-dopa and 2% NaCl; three formulations included 29% w/w HPMC and 1% w/w maltoside (prepared by small modifications of the spray drying process) and two formulations contained 29.9% w/w HPMC with 0.1% w/w maltoside or 29.5% HPMC with 0.5% w/w maltoside. Each group (N=4) received four oral 5 mg benserazide pre-treatments at -24, -16, -8 and -0.75 hours before L-dopa formulation delivery by the nhpPOD Device. All formulations tested achieved similar AUC and C_{max} levels compared to the third monkey PK study. Compared to the formulation in the third monkey PK study containing 7% maltoside, median T_{max} was slightly delayed (<2.3-fold, range 37.5-68 minutes across all groups compared to 30 minutes). However, while T_{max} was slightly delayed, individual plasma levels following the Group 3 formulation (29% HPMC with 1% maltoside) increased rapidly and more consistently to achieve levels >400 ng/mL L-dopa within 15 minutes. This formulation was selected for GMP manufacture and for inclusion in the proposed clinical study.
- Study 5: A PK and safety study of the nasal administration of L-dopa powder formulation containing carbidopa (Study 2037-017, N=20), in the absence of an orally administered DCI, demonstrated plasma exposures similar to the above referenced monkey PK studies (2037-003, 2037-004, 2037-006, 2037-007) where formulations of levodopa were nasally administered after administration of an oral DCI (benserazide). Maximum plasma concentration (C_{max}) of 560 ng/mL - 1,608 ng/ml were achieved following 20 mg L-dopa administration with median T_{max} between 38-68 minutes. The group receiving a formula the same as the formula to be used in Cohorts 4-5 (BG54-126; levodopa: carbidopa: HPMC: maltoside:NaCl (68: 6.8: 22.2: 1: 2) resulted in an AUC of $149,941 \pm 22,112$ ng*min/ml, a C_{max} of $1,608 \pm 198$ pg/ml, and a T_{max} of 53 minutes. These values are similar to the levodopa alone formulation administered in the above reference monkey study 2037-007 in which a formula representative of that being used in Cohorts 1-3 of the clinical study resulted in an AUC of $92,404 \pm 18,094$ ng*min/ml, a C_{max} of $1,310 \pm 413$ pg/ml, and a T_{max} of 53 minutes.

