Once dosing has been completed (for all subjects) in a cohort, data will be collected through to 7 days post dosing (Visit 4, follow-up). This data will then be reviewed by a Safety Monitoring Committee (SMC) for cohorts 1 and 2 only, and if no INP103 or placebo-related serious adverse events (SAEs) or severe AEs have been reported, dosing may commence in the next cohort. The SMC will have 7-14 days between dosing of cohorts to review safety and available PK data compiled by the site and the biostatistics analysis provider.

Interim analysis of data will be conducted upon completion of Cohort 1 and 2 study procedures, at the discretion of the Sponsor, depending on rate of recruitment. In this scenario, Cohort 1 and 2 data will be soft-locked, treatment assignment will be unblinded (limited to CNS staff; Impel staff will remain blinded) and tables, listings and figures of selected collected data will be produced. Unblinding of Cohort 1 and 2 data will not jeopardise blinding of any enrolled Cohort 3 (or subsequent Cohort) subjects at the time of the interim analysis.

Figure 1: Study Design

Cohort 1: INP103 35 mg (n=6); placebo (n=2)

Cohort 2: INP103 70 mg (n=6); placebo (n=2)

Cohort 3: INP103 140 mg (n=6); placebo (n=2)

Cohort 4: INP103 70/7.0mg (n=6, max 9); placebo (n=2, max 3)

Safety Monitoring Committee 1

Safety Monitoring Committee 2

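### No Cohort 3 finding can trigger the planned safety committee meeting before Cohort 4, and half of the reason for omitting that meeting compares doses that have no common scale

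*Protocol*

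**What the plan says.** Protocol section 8.1 states the rule: "No SMC meeting is planned following Cohort 3, unless safety concerns were raised during the SMC meetings occurring after Cohorts 1 and 2". The synopsis (Treatment Groups) repeats it: "There will be no SMC meeting between Cohorts 3 and 4 if there are no safety concerns raised by the SMC meetings" held after Cohorts 1 and 2. The reason follows: "since the dose of L-dopa and DCI in Cohort 4 is less than Cohort 3". Both places add that other usual safety monitoring continues.

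The order of events is in the synopsis (Study Design): "Cohorts will be enrolled and dosed in sequence". On moving up a dose it says: "Escalation to the next higher dose cohort (Cohorts 1 to 2 and 2 to 3) may only commence after review and approval". The reviewing body is the SMC, and what it looks at is safety data.

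Protocol section 3 describes what happens once a cohort is complete: "This data will then be reviewed by a Safety Monitoring Committee (SMC) for cohorts 1 and 2 only". Dosing of the next cohort may then begin if no treatment-related serious or severe adverse event has been reported. SAP section 4 has the same limit to Cohorts 1 and 2.

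On exposure, Protocol section 1.2.1 (Study 5) sets the monkey results for the carbidopa formula used in Cohort 4 beside those for a formula representative of Cohorts 1 to 3, and concludes: "These values are similar to the levodopa alone formulation administered in the above reference monkey study 2037-007".

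**The concern.** The condition for a meeting before Cohort 4 looks back to two meetings that are over before the first Cohort 3 subject is dosed. A related severe event, or a pattern of nasal findings, in Cohort 3 therefore has no written effect on whether the committee meets. The same kind of event in Cohort 1 or 2 bears directly on whether the next cohort may start.

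Cohort 3 has the highest L-dopa dose. It is also the only completed cohort that another cohort follows without a planned committee review, in a trial whose primary objective is safety and tolerability. The interim analysis does not fill the gap, since it too covers only Cohorts 1 and 2. At stake is whether up to nine active subjects in Cohort 4 (3/4 of a maximum of 12) receive a newly combined nasal formulation before the committee has seen the Cohort 3 data. Part of the reason offered is a comparison that the documents cannot support.

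**Working it through.** **Step 1. Timing of the condition.** Inputs: synopsis Study Design and Treatment Groups; Protocol sections 3 and 8.1; SAP section 4.

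| Committee step | Data reviewed | Relative to first Cohort 3 dose |
|---|---|---|
| Meeting after Cohort 1 | Cohort 1 | Before |
| Meeting after Cohort 2 | Cohort 2 | Before (approval is a precondition) |
| Meeting after Cohort 3 | None planned; depends only on the two rows above | After |

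The truth of the condition is settled before any Cohort 3 observation exists. Its chance of being met because of a Cohort 3 event is therefore 0 at any event rate. No assumption is needed.

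**Step 2. The stated reason.** Doses are from the synopsis.

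- L-dopa: 70 / 140 = 0.50. Same drug, nasal route and device, so the statement reproduces as a nominal comparison.
- DCI: 7.0 / 25 = 0.28. The numerator is nasal carbidopa and the denominator oral benserazide. The documents give no potency or exposure conversion, so the ratio has no interpretation.

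**Step 3. Dose per nostril.** From the actuation counts:

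- Cohort 1: 35 mg, one nostril only.
- Cohort 2: 70 / 2 = 35 mg.
- Cohort 3: 140 / 2 = 70 mg.
- Cohort 4: 70 / 2 = 35 mg.

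Protocol section 1.2.1 gives local concentrations of 0.4375 to 0.875 mg/cm² "following doses of 35–140 mg L-dopa to the nose". These fit one implied area: 35 / 0.4375 = 70 / 0.875 = 80 cm². Only Cohort 3 reaches the upper value. For L-dopa, Cohort 4 returns to the local dose of Cohorts 1 and 2.

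**Step 4. Monkey figures (secondary support only).** Protocol section 1.2.1, Study 5, carbidopa formula over L-dopa-only formula:

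- AUC: 149,941 / 92,404 = 1.62.
- Cmax: 1,608 / 1,310 = 1.23.
- Tmax: 53 minutes for both.

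Multiplying by the dose ratio of 0.50 gives Cohort 4 exposure of about 0.81 (AUC) and 0.61 (Cmax) of Cohort 3. This assumes equal monkey doses, dose-linearity and carry-over to humans. The 20 mg dose is stated only for the carbidopa study, and the two formulas come from different studies.

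**Step 5. Units.** Study 5 prints 1,608 as ng/ml in one sentence and as pg/ml in another. In ng/ml, AUC / Cmax = 149,941 / 1,608 = 93 minutes, which is plausible. In pg/ml it would be 149,941 / 1.608, or about 93,247 minutes. The pg/ml unit conflicts with the rest of the paragraph.

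**The case against.** The strongest reply is that Cohort 4 is a step down. It repeats the L-dopa dose and the one-spray-per-nostril regimen of Cohort 2, which the committee does review. The L-dopa half of the reason is like for like. The committee consists of the Principal Investigators and two medical monitors, and the investigators already grade every event as it occurs. Serious events go to the CRO within 24 hours (section 8.3.1), and the sponsor, investigator or ethics committee may suspend the study at any time (section 10). All of this stands and limits how serious the point is. It does not supply a planned joint review of Cohort 3. The 24-hour route covers serious events, not severe non-serious ones, and suspension is discretionary. Nor does the Cohort 2 comparison cover nasal carbidopa, which is first given in Cohort 4.

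Three stronger readings are tempting and are not supported.

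- *No Cohort 3 event could lead to any review.* Section 8.1 says only that no meeting is planned, so an ad hoc meeting is not forbidden. Nor would an event in Cohort 1 or 2 automatically hold the next cohort: section 3 has an event criterion, but section 8.1 lets the committee proceed on an acceptable benefit:risk judgement.
- *Cohort 4 may be exposed to more L-dopa than Cohort 3.* The AUC ratio is cross-study with no comparator dose stated, and both scaled point estimates stay below 1. Study 6 gave carbidopa formulations with Cmax values of 899 to 1,167, which is 0.69 to 0.89 of 1,310 (dose not stated, and printed in an AUC unit), with no safety signal. The waiver does not cite the monkey data in any case.
- *There is a known chance of a missed event.* The documents give no event rate. With six active subjects, 1 − (1 − p)^6 runs from 26.5% at an assumed p of 5% to 88.2% at 30%, so the figure mostly reflects the assumption.

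**Conclusion.** The point holds in a limited form and should be fixed. Under the written rule, no Cohort 3 finding can trigger the planned committee meeting before Cohort 4. That follows from the order of events alone.

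The reason for the waiver is half sound. The L-dopa comparison (0.50) is valid as a nominal dose comparison, while the DCI comparison has no common scale and says nothing about local tolerability of the combined formulation. The monkey ratios of 1.62 and 1.23 show only that equal milligrams need not mean equal exposure, subject to the assumptions in step 4. They do not show that Cohort 4 is at higher exposure than Cohort 3. The remaining safeguards and the step down in L-dopa dose keep this below a defect that would by itself stop the trial.

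**What to change.** Reconcile the synopsis (Study Design and Treatment Groups), Protocol sections 3 and 8.1, and SAP section 4, so that the condition for a committee meeting before Cohort 4 can take account of Cohort 3 safety data already being collected. Alternatively, state why it need not. The waiver should not rest on the milligram comparison between two inhibitors given by different routes. The content of any safety rule is for the sponsor to decide.

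As an editorial matter, section 1.2.1 should report the AUC and Cmax ratios beside the word similar, state the comparator dose and resolve the Cmax units.

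The committee already exists, so the cost is wording and possibly a short pause before Cohort 4. For scale, the protocol allows the committee 7 to 14 days between the earlier cohorts.

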8.2. Definition of an Adverse Event

An AE is any event, side-effect, or other untoward medical occurrence that occurs in conjunction with the use of a medicinal product in humans, whether or not considered to have a causal relationship to this treatment. An AE can, therefore, be any unfavourable and unintended sign (that could include a clinically significant abnormal laboratory finding), symptom, or disease temporally associated with the use of a medicinal product, whether or not considered related to the medicinal product.

Events meeting the definition of an AE include:

- Exacerbation of a chronic or intermittent pre-existing condition including either an increase in frequency and/or intensity of the condition

- New conditions detected or diagnosed after INP103, or placebo administration that occur during the AE reporting periods, even though it may have been present prior to the start of the study
- Signs, symptoms, or the clinical sequelae of a suspected interaction
- Signs, symptoms, or the clinical sequelae of a suspected overdose of either INP103 or placebo or a concomitant medication (overdose per se will not be reported as an AE/SAE)

Events that do not meet the definition of an AE include:

- Medical or surgical procedure (e.g., endoscopy, appendectomy); the condition that leads to the procedure should be reported as an AE if it meets the criteria of an AE
- Situations where an untoward medical occurrence did not occur (e.g., social and/or convenience admission to a hospital)
- Anticipated day-to-day fluctuations of pre-existing disease(s) or condition(s) present or detected at the start of the study that do not worsen

If there is evidence of an AE through report or observation, the Investigator or designee will evaluate further and record the following information:

- Time of onset and resolution
- Severity
- Causality/relation to study treatment
- Action taken regarding INP103 or placebo
- Outcome

8.2.1. Severity of an Adverse Event

Severity of adverse events will be graded by the Investigator as one of:

- **Mild:** A type of AE that is usually transient and may require only minimal treatment or therapeutic intervention. The event does not generally interfere with usual activities of daily living
- **Moderate:** A type of AE that is usually alleviated with additional specific therapeutic intervention. The event interferes with usual activities of daily living, causing discomfort but poses no significant or permanent risk of harm to the research subject
- **Severe:** A type of AE that interrupts usual activities of daily living, or significantly affects clinical status, or may require intensive therapeutic intervention

8.2.2. Causal Relationship of an Adverse Event

The Investigator will assess the relationship between INP103 or placebo and the occurrence of each AE. The Investigator's assessment of the relationship of each AE to investigational product will be recorded in the source documents and the eCRF. Alternative causes, such as medical history, concomitant therapy, other risk factors, and the temporal relationship of the event to INP103, or placebo administration should be considered and investigated, if appropriate. The following definitions are general guidelines to help assign grade of attribution:

- Not related: The event is clearly related to other factors such as the subject's clinical state, therapeutic interventions or concomitant drugs administered to the subject. This is especially so when an event occurs prior to the commencement of treatment with INP103 or placebo.
- Unlikely: The event was most likely produced by other factors such as the subject's clinical state, therapeutic interventions, or a concomitant drug administered to the subject and does not follow a known response to INP103 or placebo.
- Possible: The event follows a reasonable temporal sequence from the time of INP103 or placebo administration or follows a known response to INP103 or placebo but could have been produced by other factors such as the subject's clinical state, other therapeutic interventions, or concomitant drugs administered to the subject.
- Probable: The event follows a reasonable temporal sequence from the time of INP103 or placebo administration and follows a known response to INP103 or placebo and cannot be reasonably explained by other factors such as the subject's clinical state, other therapeutic interventions, or concomitant drugs administered to the subject.

